## 9.1. Adverse Events

An AE is defined as any untoward medical occurrence in a patient or clinical investigation subject administered a pharmaceutical product and that does not necessarily have a causal relationship with this treatment. An AE can therefore be any unfavorable or unintended sign (including an abnormal laboratory finding), symptom, or disease temporally associated with the use of a medicinal (investigational) product, whether or not related to the medicinal (investigational) product. In addition, during the screening period, AEs will be assessed regardless of the administration of a pharmaceutical product.

Adverse events will be assessed, documented, and recorded in the eCRF and will be classified by SOC and PT according to MedDRA version 16.0 or higher throughout the study (ie, after informed consent has been obtained). All AEs collected from the time of informed consent that are prior to study treatment will be defined as pretreatment AEs and will be presented in the listings.

A TEAE is defined as an AE that meets any of the following conditions:

- Begins on or after the first dose of study drug and before the final scheduled office visit at Week 36;
- Begins before the first dose of study drug and worsens in severity on or after the first dose of study drug and before the final scheduled office visit at Week 36;
- Is completely missing an onset date and the end date is on or after the first dose of study drug

If a patient receives BOTOX after receiving topiramate, the physician will be asked to determine if the AE is due to BOTOX or topiramate or unknown.

For the purpose of inclusion in TEAE tables, incomplete AE onset and end dates will be imputed as follows:

Missing onset dates (where “UK” and “UKN” indicate unknown or missing day and month respectively):

- UK-MMM-YYYY: If the month and year are different from the month and year of the first dose of study drug, assume the onset date is 01-MMM-YYYY. If the month and year are the same as the first dose of study drug month and year, and the end date (after any imputation) is on or after the first dose of study drug, then assume the onset date is the date of the first dose of study drug. If the month and year are the same as the first dose of study drug month and year and the end date (after any imputation) is prior to the first dose of study drug, then assume the end date for the onset date.
- DD-UKN-YYYY/UK-UKN-YYYY: If the year is different from the year of first dose of study drug, assume 01-JAN-YYYY of the collected year. If the year is the same as the first dose of study drug year, and the end date (after any imputation) is on or after the first dose of study drug, then assume the onset date is the date of the first dose of study drug. If the year is the same as the first dose of study drug, and the end date (after any

imputation) is prior to the first dose of study drug, then assume the end date for the onset date.

Missing end dates (where “UK” and “UKN” indicate unknown or missing day and month respectively):

- UK-MMM-YYYY: Assume the end date is the last day of the month;
- DD-UKN-YYYY/UK-UKN-YYYY: Assume the end date is 31-DEC-YYYY.

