## 9. Safety Analyses

All analyses of safety will be conducted using the Safety Set. All patients will be summarized according to the treatment they actually received, but the subgroup of topiramate patients who initially received topiramate and then switched to BOTOX will be summarized as follows:

- All safety assessments occurring prior to the date of the first dose of BOTOX will be summarized for the topiramate treatment arm.
- All safety assessments except AEs occurring on or after the date of the first dose of BOTOX will be summarized separately for the topiramate + BOTOX subgroup. For all AEs, the total number of patients (N) in each treatment arm will represent the number of patients that received that treatment. A patient may be counted in both treatment arms. The overall total will be the number of patients that received any treatment. The topiramate + BOTOX treatment arm will be a subset of the BOTOX treatment arm and will include patients that received both treatments. Denominators for percentages will be the total number of patients in each treatment arm or overall. Treatment-emergent AEs (TEAEs) include all AEs that start on or after the first dose of study medication up to the final visit, or are present prior to the first dose but increase in severity after the first dose of study medication up to the final visit. For patients who switch from topiramate to BOTOX, TEAEs starting on or after the date of the first BOTOX injection will be counted in the treatment arm that they are related to, as determined by a physician. If the TEAE is related to both treatments or if the relationship is unknown, it will be counted in both treatment arms but only once in the total. The topiramate + BOTOX subset will summarize all TEAEs that occurred after a patient has switched from topiramate to BOTOX.

Statistical hypothesis testing will not be performed on any safety results

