### **9.1.1. Incidence of Adverse Events**

All AEs will be summarized for the Safety Set in the manner described in Section 9. Counts and percentage of patients with each type of AE will be provided. Denominators for percentages will be the total number of patients treated in each arm or overall. At each level of patient summarization, a patient is counted once if the patient reported one or more events.

An overview summary of the number and percentage of patients with any TEAE, serious TEAE, study drug-related TEAE, study drug-related serious TEAE, TEAE leading to treatment discontinuation, TEAE leading to study discontinuation, and AE leading to death will be provided by treatment arm.

Treatment-emergent AEs will also be summarized separately for each injection cycle for BOTOX treated patients.

The following summary tables will be repeated for any TEAE, serious TEAE, study drug-related TEAE, study drug-related serious TEAE, TEAE leading to treatment discontinuation, TEAE leading to study termination, and AE leading to death.

Summaries of the total number of TEAEs and the number and percentage of patients with at least one TEAE will be provided by treatment group. The number and percentage of patients and the number of events will also be presented by SOC and PT in descending order from the SOC with the highest total incidence (that is, summed across all treatment groups) to the SOC with the lowest total incidence. If the total incidence for any 2 or more SOCs is equal, the SOCs will be presented in alphabetical order. Within each SOC, the PTs will be presented in alphabetical order. At each level of patient summarization, a patient is counted once if the patient reported one or more events.

All AEs, will be presented in a by-patient listing.

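### SAP 9 and SAP 9.1 end the treatment-emergent AE window at different visits; under 9.1, switchers' fully dated AEs from Week 36 to Week 48 drop out of the TEAE tables

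*SAP*

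**What the plan says.** SAP 9 says that TEAEs "include all AEs that start on or after the first dose of study medication up to the final visit", and gives the same end point for AEs that increase in severity. It names no week.

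SAP 9.1 then gives a formal three-part definition. A new AE qualifies if it "Begins on or after the first dose of study drug and before the final scheduled office visit at Week 36". A pre-existing AE qualifies if it worsens within that same window. The third condition has no Week 36 limit but covers only AEs whose onset date is completely missing.

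For patients who stop topiramate and move to BOTOX, SAP 3.1, 3.4 and 7.2 schedule injections at Week 12, 24 or 36, with the exit visit at Week 48. For everyone else Week 36 is the planned last visit.

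The tables at issue are described in SAP 9 and 9.1.1:

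- "The topiramate + BOTOX subset will summarize all TEAEs that occurred after a patient has switched from topiramate to BOTOX"
- "Treatment-emergent AEs will also be summarized separately for each injection cycle for BOTOX treated patients"
- On layout, "All AEs will be summarized for the Safety Set in the manner described in Section 9"

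SAP 1 says the plan serves both the Week 36 analysis and the final analysis. It assigns no separate TEAE rule to either. SAP 11, on departures from the protocol, does not mention the point.

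**The concern.** The two definitions agree for patients who exit at Week 36, apart from onsets on the visit day itself. They differ for switchers, whose last visit is 12 weeks later. Two programmers working from this SAP could therefore produce different TEAE tables, and each could cite a section in support.

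If 9.1 is coded, percentages in the BOTOX and topiramate + BOTOX columns can only fall or stay the same, because events leave the numerator and the patients remain in the denominator. The topiramate column can lose events too. SAP 9 assigns a switcher's post-injection TEAE to the drug it is judged related to, and "If the TEAE is related to both treatments or if the relationship is unknown, it will be counted in both treatment arms". The documents therefore do not fix the direction of the effect on the between-group difference.

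That difference matters because Protocol 2.2 states a tolerability hypothesis about AE rates, and SAP 9 plans no safety test. The descriptive tables are the main evidence for it. The protocol also collects what 9.1 would discard: AEs are recorded throughout the study (Protocol 9.1.1), and patients given BOTOX are followed for 12 weeks after the last injection (Protocol 3.3).

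**Working it through.** **Inputs.** Target days from SAP Table 1: Week 12 = Day 85, Week 24 = Day 169, Week 36 = Day 253, Week 48 = Day 337. Switch visits and the Week 48 exit are from SAP 3.1, 3.4 and 7.2.

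**Length of the disputed window.** 337 − 253 = 84 days = 12 weeks. This reproduces the plan's own 12-week follow-up after a Week 36 injection. It also equals the 84 days that SAP 7.1 counts as BOTOX exposure after the last injection. SAP 7.1 sets no AE window, so this shows only that the cutoff and the exposure definition do not line up.

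**Share of post-switch follow-up lost under 9.1**, for a switcher followed to Week 48:

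| First BOTOX injection | Post-switch days | Days inside 9.1 | Days lost | Share lost |
|---|---|---|---|---|
| Week 12 | 337 − 85 = 252 | 253 − 85 = 168 | 84 | 84/252 = 33% |
| Week 24 | 337 − 169 = 168 | 253 − 169 = 84 | 84 | 84/168 = 50% |
| Week 36 | 337 − 253 = 84 | 253 − 253 = 0 | 84 | 84/84 = 100% |

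These are shares of follow-up time, not of events.

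**By-cycle table.** If cycles are numbered within each patient, a switcher reaches a third cycle only with injections at Weeks 12, 24 and 36. That cycle runs from Week 36 to Week 48, so 84 of its 84 days are excluded and switchers can contribute no fully dated TEAE to it.

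**Effect on the reported percentage (illustration).** SAP 9.1.1 counts patients, not events: "a patient is counted once if the patient reported one or more events". Assume each 12-week cycle independently gives a switcher probability p of at least one fully dated TEAE. With k post-switch cycles (k = 3, 2 or 1):

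- Section 9: 1 − (1 − p)^k
- Section 9.1: 1 − (1 − p)^(k − 1)
- Loss: p(1 − p)^(k − 1)

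Post-switch any-TEAE percentage, Section 9 vs 9.1, with the loss in points:

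| First injection | k | p = 0.10 | p = 0.20 | p = 0.30 |
|---|---|---|---|---|
| Week 12 | 3 | 27.1 vs 19.0 (8.1) | 48.8 vs 36.0 (12.8) | 65.7 vs 51.0 (14.7) |
| Week 24 | 2 | 19.0 vs 10.0 (9.0) | 36.0 vs 20.0 (16.0) | 51.0 vs 30.0 (21.0) |
| Week 36 | 1 | 10.0 vs 0 (10.0) | 20.0 vs 0 (20.0) | 30.0 vs 0 (30.0) |

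**Partial dates.** For an onset with the month unknown, SAP 9.1 says: "If the year is different from the year of first dose of study drug, assume 01-JAN-YYYY of the collected year". If the year is that of the first dose and the AE ended on or after the first dose, the onset becomes the first-dose date. Either rule can place an AE that really began after Week 36 before the cutoff. Under 9.1 that AE is then a TEAE, while the same AE with its full date is not.

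**The case against.** The strongest reply is that the SAP already points to Section 9. SAP 9.1.1 sends the reader there for the manner of summary, the later AE tables follow 9.1.1, and Section 9 holds the specific rule for switchers. Read literally, 9.1 would leave almost nothing to report for patients first injected at Week 36, whom the plan expressly provides for. The 9.1 wording looks like non-switcher text that was never extended to Week 48. This is probably right about intent, but the reference concerns how AEs are summarized, not which definition applies. Section 9.1 carries the formal definition and ties its date-imputation rules to inclusion in the TEAE tables, so a programmer could reasonably code it.

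Several narrower points stand as limits on the finding:

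- The SAP does not say how cycles are numbered for switchers. In a pooled by-cycle table the third-cycle row would not be empty, because randomized BOTOX patients' third cycle (Weeks 24 to 36) stays inside the window. The switchers' contribution would be missing without notice.
- The partial-date effect is conditional. The 1 January rule rescues an AE only if that date precedes the patient's Week 36 visit. An AE moved to the first-dose date falls in the topiramate period under either definition. An AE with only the day unknown, in a calendar month after the Week 36 visit, is also excluded.
- The percentage-point losses follow from the chosen p. At p = 0.05 they would be 0.05 × 0.95² = 4.5 to 5 points.
- The harm is confined to descriptive tables, and every AE remains in the listings.

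**Conclusion.** The concern holds. The SAP contains two TEAE definitions with different end points and does not say which governs. If 9.1 is used, the topiramate + BOTOX subset would not cover all post-switch AEs as Section 9 promises.

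Only the 84-day window and its 33%, 50% and 100% shares come from the documents, on the planned visit schedule. The loss of 8.1 to 30 percentage points applies within the switcher subset only. It rests on assumed per-cycle probabilities of 10% to 30%, independence between cycles, injection at every scheduled visit and follow-up to Week 48. No figure for the pooled BOTOX column is possible, because the number of switchers is not given.

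Efficacy, sample size, deaths and AEs with a completely missing onset date are unaffected. AE-related discontinuation of BOTOX is largely unaffected, because no injection is scheduled after Week 36. This should be fixed before the tables are programmed, but it does not threaten the primary result.

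**What to change.** In both dated conditions of SAP 9.1, replace the Week 36 cutoff with the patient's own final visit, inclusive: Week 36, or Week 48 for patients who switched to BOTOX. Tying the rule to the patient's own last visit also covers early exits. State the data cut for the Week 36 report separately, so that a reporting date is not built into the TEAE definition.

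Two small additions would close the remaining gaps: a sentence saying that Section 9 uses the 9.1 definition, and alignment of the worsening rule, which counts from after the first dose in Section 9 but from the first dose onward in 9.1.

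The core change is one phrase in two bullets and one date condition in the program. No new data are needed, because AEs are already collected to the exit visit. TEAE counts in any column that contains switchers may rise compared with a 9.1 program.

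### Partial AE onset dates are imputed from the first dose of study drug only, so in switchers some post-BOTOX events are likely to be counted under topiramate; ongoing AEs with no onset date meet no TEAE condition

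*SAP*

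**What the plan says.** **Allocation (SAP 9).** A switcher's safety findings dated before the first BOTOX dose belong to the topiramate arm. From that date, "TEAEs starting on or after the date of the first BOTOX injection will be counted in the treatment arm that they are related to", as judged by a physician; events related to both drugs, or of unknown relationship, count in both columns. The BOTOX N is everyone who received BOTOX, and topiramate + BOTOX is a subset of it.

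**Onset imputation (SAP 9.1).**
- Day unknown: "If the month and year are different from the month and year of the first dose of study drug, assume the onset date is" the first of that month. In the month of the first dose, the onset becomes the first dose date if the end date is on or after that dose, and otherwise the end date.
- Month unknown: "If the year is different from the year of first dose of study drug, assume 01-JAN-YYYY of the collected year". When the two years match and the event had not ended before treatment began, the onset becomes the first dose date.

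**End dates (SAP 9.1).** Month known: last day of the month. Only year known: 31 December. There is no rule for a wholly missing end date or an ongoing event.

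**Treatment emergence.** Worsening is judged against the first dose: SAP 9 includes events that "are present prior to the first dose but increase in severity after the first dose of study medication". The third condition in SAP 9.1 covers an event that "Is completely missing an onset date and the end date is on or after the first dose of study drug".

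**Per-cycle table (SAP 9.1.1).** "Treatment-emergent AEs will also be summarized separately for each injection cycle for BOTOX treated patients".

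**The concern.** The date that decides a switcher's arm is the first BOTOX injection, but the date used to fill in an incomplete onset is the first topiramate dose. An event that began after BOTOX can therefore be imputed to before it. It then leaves the BOTOX and topiramate + BOTOX numerators while the patient stays in both denominators.

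This bears on a stated aim. Protocol 2.2 hypothesises superior tolerability for BOTOX, measured by rates of adverse events and of discontinuations due to them. SAP 9 plans no hypothesis tests on safety, so the descriptive tables carry the comparison. BOTOX may begin during the topiramate taper (Protocol 5.4.2.2, SAP 3.4), so attribution is hardest around the switch. Office visits are 12 weeks apart, which makes an unknown onset day plausible.

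The ongoing event with no onset date is a separate gap. It would drop out of the treatment-emergent tables although the SAP is cautious with other missing items: a missing relationship is tabulated as related (SAP 9.1.2) and a missing severity as severe (SAP 9.1.3).

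**Working it through.** The plan gives no figure to reproduce. The check applies the SAP 9.1 rules literally and compares the result with the first BOTOX date.

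**Worked case.** First topiramate dose 10 March 2015; first BOTOX 84 days later, 2 June 2015.

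| Recorded onset | Imputed onset | Against 2 June |
|---|---|---|
| June 2015, day unknown | 1 June 2015 | before: topiramate |
| Year 2015 only, ending after 10 March | 10 March 2015 | before: topiramate |
| July 2015, day unknown | 1 July 2015 | after: relatedness rule |
| March 2015, day unknown, ongoing | no branch applies (needs an end date) | undefined |

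**Direction.** The imputed onset is the 1st of the month, 1 January, the first topiramate dose, or an end date that precedes that dose. None can carry an event that truly began before BOTOX to a date on or after BOTOX. The reverse can happen.

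**Switch month, month-only onset.** Assume a 30-day month with injection day and post-injection onset day uniform. There are 30 × 31 / 2 = 465 pairs with onset on or after injection, and 30 of these have the injection on the 1st. Share dated before BOTOX: 435/465 = 93.5%. A run over a four-year calendar gave 93.6%, with 0% moving the other way.

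**All post-BOTOX month-only onsets.** About 435/30 = 14.5 onset days per switcher are misdated. Assume onset uniform from first BOTOX (Day 85, 169 or 253) to Week 48, so T = 252, 168 or 84 days:
- Week 12 switch: 14.5/252 = 5.8% (calendar run 5.8%)
- Week 24 switch: 14.5/168 = 8.6% (8.8%)
- Week 36 switch: 14.5/84 = 17.3% (17.5%)

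Onsets in later months are dated after BOTOX.

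**Year-only onset.** The event is dated before BOTOX when onset falls in the calendar year of the switch, unless BOTOX was given on 1 January. The share is about 1 − (T/2)/365:
- 1 − 126/365 = 65.5% (calendar run 65.4%)
- 1 − 84/365 = 77.0% (76.9%)
- 1 − 42/365 = 88.5% (88.4%)

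These shares follow events to Week 48, as the final-visit limit in SAP 9 implies. SAP 9.1 ends treatment emergence at Week 36, and the two sections need reconciling.

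**Ongoing event, onset wholly missing.** Conditions 1 and 2 need an onset date. Condition 3 needs an end date, and no rule supplies one. No condition is met. Protocol 9.2 expects some events to be ongoing at exit.

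**Per-cycle table.** From the second injection on, a month-only onset in an injection month is dated to the 1st and falls in the previous cycle unless the injection was on the 1st. The first injection is not affected in this way. In a patient randomized to BOTOX, the first-dose branch places the event in cycle 1; a switcher has no earlier BOTOX cycle.

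**The case against.** SAP 9.1 offers its imputation for inclusion in the treatment-emergent tables, and SAP 9 does not say whether allocation uses the recorded or the imputed date. SAP 9.1 also asks the physician to attribute a switcher's event to either drug or unknown, with no date limit. Allocation of a partly dated event is therefore unspecified, and it would be too strong to say that such events are topiramate events whatever the causality. That stands. However, topiramate + BOTOX is itself a treatment-emergent summary, and SAP 9 applies attribution only to events starting on or after the injection. The imputed date is thus the natural one to use, and attribution does not clearly rescue an event dated earlier.

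A reader might also infer that every AE date rule favours BOTOX. The documents do not support that:
- The missing-onset gap can affect either arm.
- The per-cycle shift moves events between BOTOX cycles, not between drugs.
- Month-only onsets in later months are dated correctly.
- An event that began on topiramate and worsened after BOTOX stays with topiramate only if worsening does not open a new AE record, which the documents do not say.

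The consequence is bounded too. There are no safety tests, all events are listed by patient, and discontinuations due to adverse events are identified by action taken (SAP 9.1.5), not by onset date.

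**Conclusion.** The point holds in a limited form. SAP 9 allocates on one date and SAP 9.1 imputes from another. If the imputed date governs, the mismatch moves some post-BOTOX events to topiramate and none the other way. It is confined to switchers' month-only onsets in the switch month and to many year-only onsets. The percentages depend on the uniform-date assumptions shown. They are shares of partial dates, not of all events, and the documents give no count of partial dates.

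The number of switchers is also unknown. Attrition in the cited topiramate sources gives 200 × 12/96 = 25 to 200 × 54/170 = 64, but this counts patients missing from responder denominators, not switchers, and only switchers with an ambiguous date matter. The effect on the AE tables is probably small, and a material bias in the tolerability comparison is not shown. The missing-onset gap follows from the text, has no direction, and probably concerns few records. The plan should be changed because its rules misplace or lose events when followed and the repair is cheap.

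**What to change.** In SAP 9.1, with a cross-reference from SAP 9 and SAP 9.1.1:

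1. For switchers, if a partial onset is compatible with a date on or after the first BOTOX injection, and the end date (after imputation, or ongoing) does not exclude it, set the onset for allocation to that injection date. The SAP 9 relatedness rule then decides the arm. State that this date governs allocation.
2. Extend the third TEAE condition to events that are ongoing or have no end date, and treat such end dates as falling after the first dose in the onset branches.
3. State that an event which began on topiramate and worsens on or after the first BOTOX injection goes to the same relatedness rule, if worsening is not already recorded as a new event.
4. In the per-cycle table, for second and later injections, assign a month-only onset in an injection month to the cycle starting with that injection unless the end date excludes it. Year-only onsets can fit several cycles and are not covered by this step.

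The cost is SAP wording and minor programming. The downside is that some events that truly began shortly before BOTOX will be decided by relatedness and may count under BOTOX or in both columns. With an injection on the 15th of a 30-day month and uniform onset, 14/30 = 47% of that month's onsets precede it and 16/30 = 53% do not. Under the new rule, events judged related to topiramate alone still count only there.
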